- Throughout: Removed “consecutive” from CD4 eligibility criterion in all instances per Letter of Amendment #1
- Throughout: Clarified Inclusion Criterion 2 (“HIV infection documented by a plasma HIV RNA viral load, rapid HIV test or any licensed ELISA test; and confirmed by another test using a different method including but not limited to such as a rapid HIV test, Western Blot, HIV culture, HIV antigen, or HIV pro-viral DNA at any time prior to study entry”).
- Throughout: Clarified Exclusion Criterion 3 (“Presence of HIV progression such as oral thrush, unexplained weight loss, or unexplained fever at randomization”).
- Throughout: Clarified Exclusion Criterion 7 (“Diagnosis History of decompensated liver disease before randomization”).
- Throughout: Added “Fractures” as a secondary outcome. NOTE: This is not a new data collection item, simply adding an already-collected event to the list of secondary outcomes.
- Throughout: Took out references to substudy data collection (e.g., in Section 3.7.3, “In a subset of participants, neuropsychological tests...”), as these are in the substudies themselves.
- Section 1 (Synopsis/Rationale), Section 2.2.1 (previously “Treatment Guidelines”, now “Current evidence and practice on the timing of ART initiation”) and following: Rewritten to highlight where evidence from randomized trials is available to inform practice and de-emphasize dependence on guidelines. References added.
- Section 3.7.4 (Participant Follow-up): minor changes to better reflect data being collected at follow-up time points.
- Section 3.8.4 (Reporting Serious Events) and Section 4.1.8 (Abacavir Hypersensitivity Reaction): Removed references to a separate CRF for reporting abacavir hypersensitivity reactions to GSK. GSK have agreed to accept our Form 400 (Serious Event), on which all ABC hypersensitivity reactions must be reported, as sufficient for their purposes.
- Section 4.2 (CD4+ Cell Count and Viral Load Monitoring): Incorporated language regarding appropriate clinical management for participants in the deferred group whose CD4+ cell count is declining, per Jan 2010 communication to investigators.
- Sections 8.3.10 and 8.3.11 (Sample Size Estimation and Data Analysis, respectively, for the Informed Consent Substudy): Modified after performing the planned sample site re-estimation at the end of the pilot phase.
- Main study consents (Appendices A-1 and A-7): Incorporated language regarding updated US guidelines in consents per Jan 2010 communication to investigators.
- Main study consents: Modified language to permit sites to use a single consent for the main study that includes permission to collect and store specimens. A separate consent for specimen storage is still available (Appendix A-2); its signature page has been updated.

- Genomics Substudy consent, “What do you have to do if you are in the Genomics Substudy?”: corrected error in amount of blood to be drawn (9 mL instead of 6 mL; 6 mL is the amount being *stored*).
- Other consents: Incorporated Clarification Memos in regard to malignancy specimen collection (Appendix A-3), Genomics substudy involuntary withdrawal (Appendix A-4), and contraceptive language in main study Concise consent (Appendix A-7).
- Appendix C (Time & Events Schedule): Removed substudy data collection items, as there are now substudies open which are not included in the main protocol document. A Time & Events Schedule which includes data collection items for all substudies will be maintained on the INSIGHT website in a format that will allow sites to download it and delete items for those substudies in which they are not participating.
- Appendix D: Deleted INSIGHT Executive Committee (no longer exists). Updated START protocol team membership.

Summary of additional changes to START protocol Version 2.0, dated 25 October 2010

1. References to international regulatory documents (Declaration of Helsinki, EU clinical trials directives) modified to refer to “current version” rather than a specific version that may have since been updated. (Clarification Memo, 17 February 2011)
2. As planned, the sample size was re-estimated before enrollment was completed. Section 5.3 is added to the protocol to detail the updated sample size and primary event target. The inclusion criterion for age is changed to 35 years or older after 4,000 participants are enrolled to increase the likelihood of primary endpoints. (Letter of Amendment 2, 14 February 2013)
3. To comply with changes in EU guidance and individual country laws, language is added requiring reporting of serious adverse events within 24 hours following investigator knowledge of the event, for sites in EU member states. (Letter of Amendment 2.1, 13 May 2013)

Analysis Plan Informed Consent Substudy (26 Oct 2013)

INSIGHT START

Purpose of the study: to evaluate understanding of study information and satisfaction with the consent process among participants of the START study after receiving information from one of two different consent forms: a standard or a concise consent form.

Hypothesis: comprehension for those receiving the concise consent form will be at least as good as for those who received the standard form. Satisfaction will be higher in the concise group.

Unit of randomization: site

Stratified randomization- grouped by primary language, and centrally assigned by block randomization within stratum

Primary endpoint- proportion of participants who answered the randomization questions correctly

Secondary endpoints-

Comprehension score (based on # of correct answers to knowledge questions)

Composite score of satisfaction

Composite score of voluntariness

There is limited info available on site to site variability in understanding randomization. Based on data from the ESPRIT study, estimated coefficient of variation for true proportions between sites was 0.30 and estimated intra-site correlation coefficient 0.09. Based on this, an estimated 58 sites are needed to show a difference of 15% between participants receiving each consent who respond accurately to questions about randomization with a power of 0.80 at the two sided level of significance of 0.05 (a total of 1450 participants). With 179 sites and 4150 participants in the substudy, our power is substantially increased, and we should be able to readily identify differences between consents in the level of understanding of randomization, even if the site-to-site variability is higher than that found in ESPRIT.

Logistic regression appropriate to cluster randomized trials will be used to compare groups for the primary outcome. Odds ratios and confidence intervals. Primary analysis will include all participants who completed the post-consent questionnaire.

Mean levels of continuous secondary outcomes accounting for within-site correlation, and using the intrasite correlation coefficient. Secondary analyses will include those who did not complete the questionnaire and count incomplete responses as incorrect responses.

Statistical analysis

Descriptive statistics by:

- two-way tables with counts and proportions for categorical variables. P-values by chi-square or exact tests
- Median (IQR) (or mean-SD in a few cases) for continuous variables. P-values by Mann-Whitney/Kruskal-Wallis tests (or t-test/one way ANOVA respectively)
- Results shown by arm (i.e. consent assignment)

Univariable/multivariable analysis– *Correct answer to randomization question, Question A.6 (somewhat/very satisfied vs. other), Question A.26 (Could have refused to join START yes vs. no)*

- Multi-level logit models with random site effects (Stata's xtmelogit)
- Results of univariable models shown only if global Wald test was significant at the 0.20 level
- Model results shown as Odds Ratios and as %Risk differences
- In both cases, all comparisons are relative to the respective baseline category (usually the most prevalent).
- Continuous variables centered at the mean of their overall distribution thus risk differences
- in the case of continuous variables are relative to a typical person with the covariate of interest at the mean level.
- Risk differences and respective 95% CIs estimated through the Delta method (i.e. Stata's nlcom) and based on the estimate beta coefficients of the fixed effects and their variance-covariance matrix

Univariable/multivariable analysis– *Comprehension Score (0-16) and Satisfaction Score (0-8)*

- Quantile (median) regression with corrected SEs for clustering within sites (Stata's qreg2 - Parente, P.M.D.C. and Santos Silva, J.M.C. (2013), Quantile regression with clustered data, Department of Economics, University of Essex, Discussion Paper No 728.)
- Results of univariable models shown only if global Wald test was significant at the 0.20 level
- Model results shown as beta coefficients. All comparisons are relative to the respective baseline category (usually the most prevalent).

Univariable/multivariable analysis– *Voluntariness Score (0-4)*

- Ordinal logistic regression with corrected SEs for clustering within sites (Stata's ologit)
- Results of univariable models shown only if global Wald test was significant at the 0.20 level
- Model results shown as Odds Ratios (for higher scores)
- All comparisons are relative to the respective baseline category (usually the most prevalent).
- Due to violations of the proportionality of odds assumption, the dependent variable was recoded into a binary one (4 vs. <4) and logistic models were fitted (only for the multivariable models identified using the ordinal logistic regression)

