8.3.6 Randomization of Participating Sites

For scientific reasons, to minimize contamination, the unit of randomization will be the site rather than the individual participant. Sites will have the option of participating in the consent substudy. Sites that choose not to participate in the substudy will use the standard consent template. Sites that choose to participate in the substudy will submit both the standard and concise forms to their IRB. All reviewing IRBs/IECs will be informed that the consent documents are part of a randomized assessment of understanding and asked to consider minimizing stipulated changes to the consent documents. After IRB/IEC approval, the site will register to START and the Informed Consent substudy and will submit both consents for approval, as per usual procedures. The Informed Consent substudy team will review any changes made to consent documents to ensure that the two documents remain sufficiently different. Similar processes will be followed for any amendments to the consent if the protocol changes.

After registration, the site will be randomized to either the standard form or the concise form. A stratified randomization scheme will be used. Eligible sites will be grouped by primary language of participants, and sites will be centrally assigned to use the concise or standard consent (1:1 allocation) by block randomization within stratum. The site will be notified of their consent form assignment when they receive notification from the SDMC that they are open to randomize participants to START.

The substudy will randomize by site in order to enhance the ability to compare the two consent documents and decrease the possibility that those obtaining consent will alter their usual process because of the substudy. Additionally, randomization by site will minimize the logistical burden at the site because the same consent form and process will be utilized for each participant.

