Sample size for the START substudy is estimated using an approach described by Hayes and Bennett.¹⁰⁷ They use the between-site coefficient of variation (standard deviation divided by mean) to estimate sample size. Their approach is equivalent to use of the intra-site correlation coefficient. If a coefficient of variation of 0.30 is assumed and each site enrolls 25 participants, then 58 sites (29 assigned to use the concise consent and 29 assigned to use the standard consent) are required to detect a difference of 15% of participants responding accurately to the questions concerning randomization (50% versus 65%) with power of 0.80 at the two-sided level of significance of 0.05 (i.e., a total of 1,450 participants). If the coefficient of variation is 0.20, then a total of 34 sites are needed with these assumptions (850 participants). For comparison, if participants were individually randomized, a total of 340 participants would be required.

Sample size assumptions were assessed after approximately 500 participants were enrolled by 70 sites; the coefficient of variation was 0.17. Most of the participants enrolled had a primary language of English, Spanish or German. Since there is interest in obtaining data for other primary languages (e.g., Thai, Greek, Portuguese), for sites in developing countries, and for other subgroups, and since the substudy has proven to be very acceptable to participants and site staff, the Informed Consent substudy decided to offer new sites in START the opportunity to participate in the substudy. This will enhance the generalizability of the substudy.

Given the current site participation and enrollment per site, it is estimated that 125-150 sites will participate in the substudy with an average enrollment of 15 participants (an estimated 2,000 participants). This will provide greater than 90% power for the primary endpoint comparison related to comprehension of randomization and allow reliable comparisons between the standard and concise groups for other measures of comprehension that are being assessed as well as subgroups of interest.

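### The p-values on the descriptive by-arm tables of the informed-consent substudy ignore site randomisation; the modelled outcomes do not have this fault.

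*Supplement*

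**What the plan says.** Protocol 8.3.6 states that "the unit of randomization will be the site rather than the individual participant", and the substudy analysis plan of 26 October 2013 repeats it: "Unit of randomization: site". Assignment is blocked within primary-language strata.

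The plan's statistical analysis section opens with descriptive statistics. Categorical variables get "two-way tables with counts and proportions for categorical variables. P-values by chi-square or exact tests". Continuous variables get medians or means, with "P-values by Mann-Whitney/Kruskal-Wallis tests (or t-test/one way ANOVA respectively"). The display is fixed by the line "Results shown by arm (i.e. consent assignment"). None of these lines mentions clustering or says that the p-values are for description only. The plan does not list which variables the tables will hold.

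The model-based analyses follow, and each is described as allowing for site. The randomisation question, A.6 and A.26 get multi-level logit models with random site effects. The comprehension and satisfaction scores get median regression, and the voluntariness score ordinal logistic regression, both with standard errors corrected for clustering. Protocol 8.3.11 likewise asks for hierarchical models for the primary outcome and for methods that respect within-site correlation for continuous secondary outcomes.

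**The concern.** When sites are randomised, two participants at one site share the same form and the same staff and setting. A chi-square, Mann-Whitney or t-test between arms counts them as independent, so the standard error is too small and the p-value too low for any variable that varies between sites.

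The plan's six modelled outcomes are protected. A tabulated questionnaire item outside those six is not: the unadjusted by-arm test is the only p-value the plan specifies for it. Yet protocol 8.3.10 says that the enlarged substudy will allow reliable comparisons of the two forms on other measures of comprehension. For a modelled outcome that also appears in a table, the reader could meet two p-values for one comparison, only one of them valid.

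**Working it through.** **Inputs**
- Sites and participants (analysis plan): "With 179 sites and 4150 participants in the substudy, our power is substantially increased". Mean site size m = 4150/179 = 23.18.
- Planning values, from the consent substudy of an earlier international trial (analysis plan; protocol 8.3.10): "estimated coefficient of variation for true proportions between sites was 0.30 and estimated intra-site correlation coefficient 0.09".
- The substudy's own check (protocol 8.3.10): "Sample size assumptions were assessed after approximately 500 participants were enrolled by 70 sites; the coefficient of variation was 0.17".
- Design target (protocol 8.3.10): 50% versus 65%, 25 per site, two-sided 0.05, power 0.80.

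**Reproducing the plan's figures**

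The Hayes-Bennett formula for sites per arm, with k the between-site coefficient of variation, is

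c = 1 + (z_α/2 + z_β)² × [p0(1−p0)/m + p1(1−p1)/m + k²(p0² + p1²)] / (p0 − p1)²

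- k = 0.30, m = 25: 1 + 7.849 × (0.0100 + 0.0091 + 0.0605)/0.0225 = 28.8. That is 29 per arm, 58 sites and 1,450 participants, as stated.
- k = 0.20: c = 17.05, which gives the stated 34 sites when rounded to the nearest whole site per arm.
- Individual randomisation, two-proportion formula: 340 in total, as stated.
- ICC = k²p/(1−p) = 0.30² × 0.5/0.5 = 0.09, as stated.

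So the plan's own sizing accepts the clustering that the descriptive tests leave out.

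**True error of an unadjusted 5% test**

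Design effect DE = 1 + (m − 1) × ICC; true α = 2 × [1 − Φ(1.96/√DE)].

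| Clustering | ICC | DE | SE understated by a factor of | True α | Simulated α |
|---|---|---|---|---|---|
| Planning value | 0.09 | 2.997 | 1.73 | 25.8% | 25.7% |
| CV 0.17, p = 0.50 | 0.17² × 0.5/0.5 = 0.0289 | 1.641 | 1.28 | 12.6% | 12.4% |

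The simulation drew beta-binomial data for 179 equal sites, 20,000 runs per row.

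**How far the range depends on its assumptions**
- ICC of other variables: the documents give none. Assumed ICCs of 0.005, 0.01 and 0.02 give 6.3%, 7.6% and 10.3%.
- Unequal site sizes: the documents do not give the spread. With an assumed coefficient of variation of site size of 0.6, simulated error is 15.2% at ICC 0.0289 and 30.8% at ICC 0.09.
- Proportion correct: the documents give no pooled proportion with the 0.17, so p = 0.50 is carried over from planning. At p = 0.65 the ICC is 0.0289 × 0.65/0.35 = 0.054, DE is 2.19 and true α is 18.5%.
- Language strata: not modelled. If part of the between-site variation lies between languages, stratified assignment balances that part and the error is lower than shown.

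**The case against.** The strongest reply is that these tests appear only under descriptive statistics. Every named endpoint and both named single items have a site-adjusted analysis, and protocol 8.3.11 requires one for the primary and the continuous secondary outcomes. On this view the by-arm p-values are decoration in an ancillary substudy, and no result of the main trial depends on them. The inflation figures also come from one variable, the randomisation question, which is itself modelled correctly, and the upper figure uses an ICC from another trial. Removing p-values from baseline tables is partly a reporting convention.

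Most of this stands. It limits the reach and severity of the point, and it makes the range conditional. It does not make the p-values right. The plan names cluster handling for each family of regression models and leaves it out here. It does not call these p-values non-inferential, and for items outside the six modelled outcomes it offers no other.

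A reader might infer that the plan compares the consent arms by unadjusted tests, or that the by-arm tables are bound to show false differences. The documents support neither. The main comparisons allow for site, and even at ICC 0.09 about 74% of true-null comparisons would come out non-significant.

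**Conclusion.** The point holds for the descriptive by-arm p-values only. For a variable that clusters like the randomisation question, their true type I error at a nominal 5% is about 13% to 26%. That range assumes 23.2 participants at every site, p = 0.50 for the lower figure, and no gain from language stratification. For other variables the size is unknown: weak clustering would bring it to about 6% to 10%, unequal sites would raise it, and stratification could lower it. The primary outcome, A.6, A.26 and the three scores are not affected. Severity is minor to moderate: the p-values are wrong as specified, but no primary or scored secondary conclusion rests on them.

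**What to change.** In the descriptive part of the analysis plan:
1. Remove p-values from by-arm tables of baseline characteristics.
2. For questionnaire items and scores, take the by-arm p-value from a model with a site random effect or cluster-corrected standard errors, or from a test on site-level summaries.
3. State that inference on the consent forms rests on the site-adjusted models.

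The cost is about two lines of wording and a small change of code. The model-based options are already in the plan and no new data are needed. The drawback is that some p-values will look less favourable.

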8.3.11 Data Analysis

The number and characteristics of sites assigned to use the standard and concise consent will be summarized. Baseline site characteristics will include primary language of participants and site staff and the background of the person administering the consent (e.g., physician, nurse, coordinator). Interested sites for which the Informed Consent substudy or sample informed consents were not approved by local ethics committees will also be summarized.

For sites participating in the Informed Consent substudy, demographic characteristics (e.g., age, gender, ethnicity) of participants consented will be compared. In addition, the number of participants at each site who refused to complete the post-consent questionnaire will be tabulated. Median (IQR) site size (number of participants consented with completed questionnaires) for each treatment group will be summarized.

Logistic regression appropriate for cluster randomized trials (hierarchical models) will be used to compare the standard and concise consent groups for the primary outcome. Odds ratios (concise versus standard consent) and 95% confidence intervals will be cited. Mean levels of continuous secondary outcomes will be compared using methods that account for the within-site correlation. The intra-site correlation coefficient will be cited for the primary and each secondary outcome.

The primary analysis will include all participants who completed the post-consent questionnaire. In a secondary analysis, participants who were consented and did not complete the questionnaire will be considered. In these analyses, participants will be counted as if they did not comprehend the consent questions.

Subgroup analyses will be conducted by primary language, the nature of differences between the standard and concise consent as judged by the Informed Consent Substudy team, age, gender, race/ethnicity, education, and previous participation in

research studies. Tests of heterogeneity will be performed to document differences among subgroups.

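### Informed Consent substudy: sites are randomised within primary-language strata, but no consent-comparison model is stated to include language, so intervals may be wider than the design allows

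*Supplement*

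**What the plan says.** **Design.** Protocol Version 2.0, section 8.3.6, groups sites by participants' primary language and states that "sites will be centrally assigned to use the concise or standard consent (1:1 allocation) by block randomization within stratum". The Analysis Plan Informed Consent Substudy (26 Oct 2013) repeats this: "Stratified randomization- grouped by primary language, and centrally assigned by block randomization within stratum".

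**Protocol analysis.** Section 8.3.11 states: "Logistic regression appropriate for cluster randomized trials (hierarchical models) will be used to compare the standard and concise consent groups". Primary language appears there as a site characteristic to be summarised and as a subgroup factor with a heterogeneity test. It is not named as a term in the main comparison.

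**Analysis plan, univariable/multivariable analysis.** The correct-answer-to-randomisation outcome is modelled by "Multi-level logit models with random site effects". The comprehension and satisfaction scores use median regression, and the voluntariness score uses ordinal logistic regression, both with standard errors corrected for clustering within sites. No covariates are listed for any multivariable model. For each group of outcomes the plan adds: "Results of univariable models shown only if global Wald test was significant at the 0.20 level".

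**The concern.** Stratified blocking balances the two consent forms across languages, so differences between languages largely cancel from the arm comparison. A model that holds the arm and a random site effect, but not language, does not know this. It assigns differences between languages to the site variance and carries them into the standard error of the consent effect.

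What is at stake is the width of the reported interval. The substudy's stated hypothesis is that comprehension with the concise form will be no worse than with the standard form. That is judged by where the interval lies, so unnecessary width weakens the conclusion. Subgroup comparisons rest on fewer sites, so width matters more there.

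A second gap does not depend on how much language matters. The plan does not say which model carries the primary comparison or which covariates enter the multivariable models, so a reader cannot tell whether language is adjusted for.

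**Working it through.** **Inputs from the documents.** Protocol section 8.3.10 gives 50% versus 65% correct, two-sided 0.05, power 0.80, 25 participants per site, planning coefficient of variation k = 0.30 (alternative 0.20), and k = 0.17 observed after about 500 participants. The analysis plan gives 179 sites and 4,150 participants, so m = 4150/179 = 23.2 per site and 179/2 = 89.5 sites per arm.

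**Step 1: reproduce the plan's figures.** Sites per arm by the Hayes–Bennett formula:

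c = 1 + (1.96 + 0.842)² × [p0(1−p0)/m + p1(1−p1)/m + k²(p0² + p1²)] / (p0 − p1)²

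- k = 0.30, m = 25: the bracket is 0.0100 + 0.0091 + 0.09 × 0.6725 = 0.0796, so c = 28.78. That rounds up to 29 per arm, or 58 sites, as stated.
- k = 0.20: c = 17.05, which is the stated 34 sites if rounded to nearest (36 if rounded up).
- Individual randomisation: 170 per arm, 340 in all, as stated.

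No language term enters these calculations.

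**Step 2: interval width with and without language.** Let R be the share of between-site variance explained by language. The documents do not give R, so it is an assumption and a range is shown.

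Variance of the risk difference = [0.25/23.2 + 0.2275/23.2 + k²(1 − R) × 0.6725] / 89.5

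Without language, the model's variance is this expression with R set to 0. For k = 0.30 that is (0.0206 + 0.0605)/89.5 = 0.000906, a 95% half-width of 5.90 points. For k = 0.17 it is (0.0206 + 0.0194)/89.5 = 0.000447, a half-width of 4.15 points.

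| R | k = 0.30: half-width with language | Unadjusted wider by | k = 0.17: half-width with language | Unadjusted wider by |
|---|---|---|---|---|
| 0 | 5.90 | 0% | 4.15 | 0% |
| 0.10 | 5.68 | 4.0% | 4.04 | 2.5% |
| 0.25 | 5.32 | 10.9% | 3.89 | 6.7% |
| 0.50 | 4.67 | 26.3% | 3.61 | 14.9% |

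**Step 3: check on the logit scale.** A random-intercept logit was simulated with 179 sites stratified over eight assumed language groups. The between-site SD was 0.6 on the logit scale (about k = 0.30 at 50%), with 200 runs per scenario and a true log odds ratio of 0.619.

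| R | Mean estimate, without / with language | Model SE, without / with | Empirical SD, without / with | Coverage, without / with |
|---|---|---|---|---|
| 0 | 0.629 / 0.629 | 0.111 / 0.109 | 0.109 / 0.109 | 95.0% / 94.5% |
| 0.25 | 0.608 / 0.611 | 0.112 / 0.100 | 0.109 / 0.109 | 95.5% / 92.0% |
| 0.50 | 0.612 / 0.615 | 0.113 / 0.090 | 0.091 / 0.091 | 98.0% / 92.0% |

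The estimate is essentially unchanged. At R = 0.50 the unadjusted SE exceeds the true spread, and the adjusted SE matches it. With 200 runs the simulation error of coverage is about 1.5 points (√(0.95 × 0.05/200)), so these runs confirm the direction but are too few to fix exact coverage. The 92.0% with language is a reason to pool very small language strata.

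**Step 4: power.** For 50% versus 65% at k = 0.30 without language, the SE is 0.0301. Power is Φ(0.15/0.0301 − 1.96) = 0.9987, or 0.9986 by the Hayes–Bennett form. It is higher at k = 0.17 or with language.

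**The case against.** Several stronger readings are tempting, and the documents do not support them.

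- **That the models hold only a random site effect.** The quoted line describes the correlation structure of a block headed univariable/multivariable analysis. The covariates are unlisted, so language is unstated rather than excluded. The score outcomes have no random site effect at all; they use cluster-corrected standard errors.
- **That the primary comparison depends on which covariates survive screening.** The 0.20 Wald rule governs which univariable results are shown. For the primary endpoint, no rule selects covariates into a model. Only the voluntariness item, which refers to multivariable models already identified, hints at selection. Read literally, though, the display rule could keep an arm-only result showing no difference out of the report.
- **That the intervals are certainly too wide.** This needs R above zero. Stratifying on language and seeking further languages make that plausible but give no value. The larger figures also use k = 0.30 from an earlier trial, whereas this substudy observed 0.17, at a time when most participants' primary language was English, Spanish or German.

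It is also fair to say that the error is conservative, that 179 sites far exceed the 58 planned, and that language is a pre-specified subgroup factor. All of this stands and keeps the point modest. A subgroup analysis does not, however, put the stratum into the main comparison, and ample power for a 15-point difference does not settle a question of no worse.

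**Conclusion.** The point holds as a conditional loss of precision and a gap in specification. The randomisation stratum is not named in any consent-comparison model. The cost in interval width runs from nothing at R = 0 to 15–26% at R = 0.50, and is 7–11% at R = 0.25, for k between 0.17 and 0.30. It rests on an assumed R, on equal site sizes of about 23, and on the planning proportions of 50% and 65%.

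The documents give no ground for inferring a biased estimate, an inflated type I error or an underpowered comparison. For the median and ordinal regressions the same conservative direction is expected, but it was not simulated. The change is worth making because it costs almost nothing and settles which model is primary.

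**What to change.** In the analysis plan:

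1. Define the primary consent comparison as consent arm + primary-language stratum (fixed effect, pooling languages with very few sites) + random site intercept.
2. Add the same language term to the planned median and ordinal regressions, keeping their cluster-corrected standard errors. They need no random intercept, and their method should not change.
3. State that this comparison is always reported, whatever the 0.20 Wald screen shows.
4. List the other multivariable covariates and label models containing them as supportive.

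The cost is a few lines of text and a few degrees of freedom out of 179 sites. Primary language is already known for every site because it defined the strata. If language explains nothing, the simulated standard error is practically the same (0.111 without, 0.109 with).
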